2.1 Number, Gender, Age and Racial/Ethnic Origin of Subjects

2.1.1 Number

It is expected that approximately 45 participants will be enrolled at NYU Langone Medical Center in order to produce 30 eligible participants at this site. Approximately 45 participants will also be enrolled at Nathan Kline Institute to produce 30 evaluable participants at that site. Participants enrolled at NYU will primarily be recruited from flyers throughout the NYU campus, internet advertisements, newspaper advertisements, recruitment emails to university mailing lists and previous studies from prior studies conducted by the lab and will directly contact the Research Coordinator for more information.

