4. Picture Ratings and practice trials on task (10-30 minutes): Subjects will be asked to rate a series of 72 images. These images include 24 OCD images from the Berlin Obsessive-Compulsive Disorder Picture Set (Simon et al., 2012), as well as 24 threat-related and 24 neutral images. Threat-related images are from the standardized IAPS database and include pictures of snarling or ferocious looking animals, weapons, and injured or distressed-looking people. Neutral images are also taken from the IAPS database and include non-ferocious looking animals, people with neutral facial expressions, and objects such as books or tables. The images (OCD, threat and neutral) will be presented in random order. After viewing each image they will make two ratings: 1. how generally negative or positive the image makes them feel and 2. how much the image evokes their OCD symptoms. This task will be performed on REDCap if the visit is remote. Ratings made during this task will be used by the research team to pick images relevant to each subject's symptoms for the SP provocation task in the scanner (see below). Subjects may also be asked to perform practice trials of the fMRI tasks during the Experiment Visits.

The entire screening procedure is expected to take from 3-4 hours, depending on the pace of the subject in answering questions, the timeliness of the medical screen appointment, and whether practice trials for the task are performed. After the Screening Visit, if the subject is deemed safe and fit to participate in the study, they will be given the option to schedule an appointment for the Baseline Visit.

Study Group Assignment after Screening Visit:

After the Screening Visit, eligible subjects will be randomly assigned into two groups: one group will receive 24 mg of ondansetron and the other group will receive placebo daily for 4 weeks. Participants will receive a 40-day supply of drug at the Baseline Visit (Day 0) and instructed to take the first dose on the following day in the morning (Day 1). The 40-day supply includes a buffer so that participation in the trial is not disrupted in the rare case that a patient needs to reschedule the Mid-Trial or Final Visits at the last minute.

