4.2 Data Analysis and Data Monitoring

(See R21/R33 application for section references)

The primary endpoints of the study are clinical symptoms and fMRI data. The specific analyses (independent and dependent variables) will be unique to each task, as described below. Safety and tolerability of 4 weeks of 24 mg ondansetron will also be evaluated.

Alpha level will be set at 0.05 for all analyses. Task-based fMRI analysis will focus on brain activation in an a priori ROI consisting of bilateral insula and somatosensory cortex, although exploratory whole-brain analyses will also be conducted. Primary group-level analyses for the R33 phase will be performed on a modified intent to treat sample consisting of participants completing at least 2 weeks of treatment. Missing data values are expected to amount to 10% or less of the data. We will consider them as MAR and impute based on a regression model. The degrees of freedom of t-tests will be adjusted appropriately. Secondary per-protocol analyses will also be conducted.

Task-based and symptoms analyses for R33:

First-level fMRI analysis: For each fMRI task, image analysis at the first (subject) level will specify separate regressors for baseline and week 4 for conditions of interest (e.g., for the "urges-for-action" task: blink suppression at baseline, blink suppression at week 4, rest at baseline, rest at week 4) to examine contrasts between baseline and week 4 (e.g., blink suppression vs. rest for baseline vs. week 4). For each task, contrasts will also examine activation during the baseline scan only (e.g., blink suppression vs. rest at baseline scan). These latter contrasts will be performed in order to measure and adjust for any baseline differences in ROI activation between ondansetron and placebo groups.

Group-level fMRI analysis: Testing for Hypothesis 2: Two-sample t-tests will compare ondansetron and placebo groups on change in activation over the 4-week trial (using first-level contrasts comparing baseline with week 4). However, if there are significant baseline differences between the groups within the insula and somatosensory ROI (using two-sample t-tests on baseline scan contrasts), standardized parameter estimates will be extracted from these regions for each subject. These parameter estimates will then be specified as covariates in follow-up one-way ANOVAs comparing ondansetron and placebo groups on change in activation from baseline to week 4 after adjusting for baseline differences.

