Relationships with clinical symptoms: Testing for Hypothesis 3a: A change score will be computed between SPS score at baseline and after 4 weeks for each subject. Two-sample t-tests will compare ondansetron and placebo groups on SPS change scores to determine whether the intervention reduces SP significantly more than placebo. In addition, change scores from baseline to week 4 will be computed for measures of overall symptom severity (using Y-BOCS and YGTSS) and compared between ondansetron and placebo groups. If there are baseline differences between the groups in any of the symptom scales (SPS, Y-BOCS, or YGTSS), follow-up one-way ANOVAs will compare change scores between ondansetron and placebo groups after adjusting for baseline scores. Testing for Hypothesis 3b: If there are significant differences between ondansetron and placebo groups in (1) SPS change scores and (2) Y-BOCS or YGTSS change scores, a Sobel test of mediation 205, 206 will investigate whether group differences in Y-BOCS/YGTSS changes are mediated by SPS changes. Briefly, mediation analyses perform a series of regressions in order to determine whether the relationship between an independent and dependent variable (e.g., treatment group and Y-BOCS/YGTSS scores) reduces significantly after including a third mediator variable (e.g., SPS score). Testing for Hypothesis 3c: If there are significant differences between ondansetron and placebo groups in (1) SPS change scores and (2) change in ROI activation or connectivity from baseline to week 4, a Sobel test will investigate whether group differences in SPS change are mediated by changes in activation or connectivity.

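### At about 60 patients the Sobel test planned for Hypotheses 3b and 3c is conservative unless both paths are large; a Monte Carlo or bootstrap interval for the indirect effect should replace it

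*Combined protocol and SAP*

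**What the plan says.** Section 4.2 (Data Analysis and Data Monitoring) names one mediation test and uses it twice.

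- Hypothesis 3b: "a Sobel test of mediation 205, 206 will investigate whether group differences in Y-BOCS/YGTSS changes are mediated by SPS changes".
- Hypothesis 3c: "a Sobel test will investigate whether group differences in SPS change are mediated by changes in activation or connectivity".

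Each test is run only if two between-arm comparisons are significant first. For 3b the condition reads "If there are significant differences between ondansetron and placebo groups in (1) SPS change scores and (2) Y-BOCS or YGTSS change scores". For 3c it is the SPS change together with "2) change in ROI activation or connectivity from baseline to week 4". In both cases the pair is the mediator and the outcome.

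The section also states "Alpha level will be set at 0.05 for all analyses". It names no bootstrap, Monte Carlo interval or joint-significance test for the indirect effect, and neither does any other part of the document. There is no power calculation, effect size or SD for the mediation analyses.

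**The concern.** The Sobel test divides the product of two estimated paths by a normal-theory standard error and compares the ratio with the normal distribution. The product of two estimates is skewed and peaked unless at least one path is estimated very precisely relative to its size. In a trial this small the ratio is therefore pulled towards zero, and the test rejects less often than its nominal level.

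Aim 3 is the part of the project that links target engagement to symptoms, and 3b and 3c are its mediation tests. A non-significant Sobel result could be read as evidence against the proposed mechanism when part of the cause is the test statistic.

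**Working it through.** **Inputs from the documents.** Section 2.1.1 plans "in order to produce 30 eligible participants at this site" (NYU) and "to produce 30 evaluable participants at that site" (NKI), so 30 + 30 = 60 in total. Section 4.1 says "eligible subjects will be randomly assigned into two groups" and gives no ratio; 1:1 is assumed here, hence about 30 per arm. Alpha is 0.05, taken as two-sided. There is no planned power figure to reproduce.

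**Algebra.** Let a be the drug effect on the mediator and b the mediator's effect on the outcome given arm, with standard errors s_a and s_b, z_a = a/s_a and z_b = b/s_b. Then

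z_Sobel = ab / sqrt(a²s_b² + b²s_a²) = z_a z_b / sqrt(z_a² + z_b²), so 1/z_Sobel² = 1/z_a² + 1/z_b².

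In absolute value, z_Sobel is always smaller than the smaller of z_a and z_b. If the two are equal, each must reach 1.96 × sqrt(2) = 2.77. If z_a = 2.2, which passes the plan's condition on the mediator, z_b must reach 1/sqrt(1/1.96² − 1/2.2²) = 4.3.

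**One scenario by hand.** Assume a drug effect on the mediator of 0.6 SD and a within-arm correlation of mediator and outcome of 0.4.

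- s_a = sqrt(2/30) = 0.258, so z_a = 0.6/0.258 = 2.32.
- Residual SD of the outcome = sqrt(1 − 0.4²) = 0.917 and s_b ≈ 0.917/sqrt(58) = 0.120, so z_b ≈ 0.4/0.120 = 3.32.
- z_Sobel at these values = 2.32 × 3.32 / sqrt(2.32² + 3.32²) = 7.70/4.05 = 1.90, which is below 1.96.
- The chance that both paths are individually significant is roughly Φ(0.36) × Φ(1.36) = 0.64 × 0.91 = 0.58.

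Simulation of the same case, ignoring the plan's conditions, gives 38% for Sobel and 56% for a Monte Carlo interval. Among trials that pass both conditions the figures are 62% and 86%.

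**Simulation model.** 30 per arm; mediator = d × arm + N(0,1); outcome = r × mediator + 0.3 × arm + noise, with within-arm outcome SD 1. All values of d, r and the direct effect of 0.3 SD are assumptions.

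**False positives.** With d = 0.8 and r = 0 (no mediation), Sobel rejects in about 1.5% of trials. The Monte Carlo and bootstrap intervals reject in 4.2% to 4.7%.

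**Power as the plan would experience it**, that is, passing both conditions and then showing mediation:

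| d (SD) | r | Sobel | Monte Carlo interval | Relative loss |
|---|---|---|---|---|
| 0.5 | 0.3 | 7.2% | 14.8% | 1 − 7.2/14.8 = 51% |
| 0.6 | 0.4 | 24.8% | 34.7% | 29% |
| 0.8 | 0.4 | 44.3% | 52.8% | 16% |
| 0.8 | 0.5 | 63.0% | 68.2% | 8% |
| 1.0 | 0.6 | 90.2% | 90.8% | 1% |

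**Share due to the conditions.** Without the conditions, the Monte Carlo interval shows mediation in 29.8%, 56.6%, 76.2% and 84.9% of trials in the first four rows (a separate run of the same model). Subtracting the table's fourth column, the conditions cost about 15, 22, 23 and 17 points. Using Sobel in place of the interval costs a further 8, 10, 9 and 5 points.

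**Cross-check.** A second simulation, with residual SD 1, direct effect 0.4 and a percentile bootstrap, agrees. For conditions plus test, Sobel against bootstrap is 8.7% against 17.0% (a = 0.5, b = 0.3), 41.9% against 53.2% (0.8, 0.4) and 90.4% against 91.4% (1.0, 0.7).

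**Smaller samples for 3b.** Section 4.1 gives the Y-BOCS to OCD patients and the YGTSS to tic patients, so either scale may cover fewer than 60. The split is not stated. In an assumed subset of 30 patients in total, the relative loss without the conditions ranged from 12% to 76%.

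**The case against.** The strongest reply has four parts.

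First, the test is never run alone. Comparisons that ignore the two significance conditions (38% against 56%) do not describe the planned procedure, and comparisons among trials that passed (62% against 86%) are not the chance of showing mediation. This stands, so the size should be judged from the table, where the largest absolute loss is about 10 points.

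Second, the conditions often limit power more than the Sobel test does. This also stands. A reader might infer that changing the test would leave 3b and 3c well powered; in the first two rows the interval still reaches only 14.8% and 34.7%.

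Third, the error is conservative. It does not create false claims of mediation, and Hypotheses 2 and 3a are untouched. This stands and limits the seriousness. It does not make a non-significant mediation result easier to interpret.

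Fourth, a bootstrap must be reconciled with the regression imputation and covariate adjustment in section 4.2. That is a fair demand on the wording, but it does not defeat the change: a Monte Carlo interval needs only the two path estimates and their standard errors.

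**Conclusion.** The point holds as a recommendation to change the test. At about 60 patients the normal approximation behind the Sobel test is poor unless both paths are large, and its false-positive rate is about 1.5% in the no-mediation case examined, against the stated 5%. Under the plan's own conditions the relative loss of power runs from almost none to about half. That range rests on 1:1 allocation, normal errors, complete data, a direct effect of 0.3 SD and path sizes that the documents do not supply.

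Two stronger readings are tempting. One is that the loss has a fixed ceiling, such as about a third. The documents give no path sizes from which to fix one, and the simulated losses fall on both sides of that figure. The other is that the Sobel test simply fails at 30 per arm. With an effect of 1.0 SD and a correlation of 0.6, the two methods differ by less than one point.

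**What to change.** In both places in section 4.2, replace the Sobel test with a 95% interval for the indirect effect (the product of the two paths). Use either a Monte Carlo interval built from the path estimates and standard errors, or a percentile bootstrap resampled within arm, with at least 5,000 resamples and any imputation repeated in each resample. Call mediation when the interval excludes zero, and report the estimate with its interval whatever the result.

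The cost is a wording change in two places and a few lines of code in SAS or MATLAB, both already listed in section 5. It needs no new data, visits or patients. The test's own false-positive rate rises from about 1.5% to about the intended 5%. With the two significance conditions in front of it, the overall rate stayed low in the no-mediation cases simulated with the bootstrap: 1.6% (a = 0.8, b = 0) and 1.5% (a = 0, b = 0.5), against 0.4% and 0.6% for Sobel.

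This change leaves the two significance conditions as they are; whether to keep them is a separate decision.

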Resting-state functional connectivity analysis: After heart rate and respiratory signals are removed from resting-"RETROICOR"207. analysis will proceed usina (www.nitrc.org/projects/conn) following our previous protocol26. Timecourses of the BOLD signal for each rest scan will be extracted from four seeds (6-mm radius spheres) in bilateral insula (two seeds in anterior and two seeds in mid-posterior insula, coordinates taken from prior work26,208). Partial correlations will be conducted between these timecourses and whole-brain gray matter, controlling for several factors. Timecourses from the top three principle components within white matter and CSF will be determined using the "CompCor" method209 and included as covariates to control for noise without having to regress out global signal210,211. Additionally, the inclusion of 12 motion variables (6 realignment parameters and first derivatives) as covariates will control for movement. Because movement is a major concern for connectivity analysis 212, we will exclude from restingstate analyses any subject moving > 1 mm or 0.5 degrees. Data will be filtered between 0.01 and 0.10 Hz213. At the first level, partial correlation coefficient images between each seed's timecourse and the whole brain will be z-transformed and compared in contrasts between baseline and week 4. For Hypotheses 2 and 3c (R33). two-sample t-tests will compare ondansetron and placebo groups in change in connectivity between baseline and week 4. As with task analyses, baseline differences will be probed using t-tests and included as covariates in follow-up ANOVAs if necessary.

Additional post-hoc analyses: Exploratory whole-brain analyses will be conducted for all contrasts of interest, correcting for multiple comparisons using cluster-level false discovery rate. For the R33 phase, we will probe for correlations between SPS score and whole-brain activation and connectivity in order to identify other future targets for treatment. We will also examine associations between other clinical measures (DOCS, PUTS, GAF)

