and ondansetron treatment as well as brain functioning. Investigation of symptom trajectories over the duration of the trial will use ANOVAs with time (baseline, week 1, 2, 3, 4) as a repeated measure. Any clinical or demographic differences remaining between the groups after randomization including age, gender, illness duration, and medication dosage (using fluoxetine equivalence) will be statistically controlled for in all analyses. For illness duration and medication, follow-up analyses will investigate the relationship between these variables and study measures (brain functioning and symptoms), not only to control for confounding but also to interrogate these variables as factors of interest.

A Data Safety Monitoring Board consisting of external scientists was assembled in August of 2015 for the R21 phase. This DSMB met every 6 months (February, August of 2016, and March 2017) via teleconference to review aggregate safety data. The board will continue to meet at this same schedule during the R33 phase. The DSMB meeting in March 2017 approved continuation to the R33 phase using the procedures described in this protocol. The board last met on December 20, 2017 (6 months after the start of the R33 phase in June of 2017) and approved the continuation of the R33 phase.

- i. The primary safety measure discussed at DSMB meetings is the incidence of adverse events, which are assessed weekly throughout the trial using the Patient-Rated Inventory of Side effects (Rush et al., 2004, Control Clin Trials, 25, 119-142). The PRISE consists of a checklist of side effects in the categories of: Gastrointestinal, Heart, Skin, Nervous System, Eyes/Ears, Genital/Urinary, Sleep, Sexual Functioning, and Other (which includes symptoms related to energy and mood). Patients endorse items and indicate whether they are tolerable or distressing. Secondarily, safety outcomes related to results from medical surveillance tests (EKG, blood test) occurring during Mid-trial and Final visits will be discussed.

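### The weekly symptom ANOVA and the Hypothesis 3a t-test rely on an unspecified regression imputation that, if single, inflates type I error; a mixed model on observed scores avoids this.

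*Combined protocol and SAP*

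**What the plan says.** All of the analysis text is in section 4.2.

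- **Trajectories.** Symptom course over the trial is examined with "ANOVAs with time (baseline, week 1, 2, 3, 4) as a repeated measure". This appears under "Additional post-hoc analyses" and tests none of Hypotheses 2, 3a, 3b or 3c.
- **Missing data.** "Missing data values are expected to amount to 10% or less of the data". Then: "We will consider them as MAR and impute based on a regression model". The predictors, the number of imputations and any pooling rule are not given.
- **Correction for imputation.** "The degrees of freedom of t-tests will be adjusted appropriately". Nothing corresponding is stated for ANOVAs.
- **Analysis set.** A "modified intent to treat sample consisting of participants completing at least 2 weeks of treatment". Patients who stop between week 2 and week 4 are therefore included, so incomplete weekly records are to be expected.
- **Hypothesis 3a.** A two-sample t-test on SPS change from baseline to week 4, with a baseline-adjusted follow-up ANOVA if the groups differ at baseline.
- **Error level.** "Alpha level will be set at 0.05 for all analyses".

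Section 4.1 schedules the SPS and the Y-BOCS or YGTSS at baseline, at the calls near days 7 and 21, at the mid-trial visit near day 14 and at the final visit. The intermediate scores therefore exist. No mixed model is mentioned.

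**The concern.** A regression prediction is not an observation. It carries no residual scatter and adds no independent information. If it is entered as one more score, the variance is estimated too low and the sample size counted too high, so the standard error is too small on both counts. Adding random residual noise to a single imputation repairs the first fault but not the second. Multiple imputation with pooling repairs both. The plan does not say which is meant, and the one correction it names does not reach the ANOVAs.

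The trajectory ANOVA is post-hoc, so on its own the consequence is limited. But the same imputation rule governs the Hypothesis 3a t-test. A significant SPS difference there is one of the two conditions for running the Sobel mediation tests of 3b and 3c, so a false positive would carry forward.

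**Working it through.** The documents give no power, SD, effect size or error rate for this analysis, so there is no stated figure to reproduce.

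**Inputs from the documents.** 30 + 30 = 60 evaluable patients across two sites; two arms; five time points; alpha 0.05; missing values at most 10%; entry to the analysis set after 2 weeks of treatment.

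**Assumptions.** 1:1 allocation, so 30 per arm; two-sided tests; equal correlation of 0.5 or 0.7 between visits; missing-at-random dropout after week 2 by the same rule in both arms.

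**Step 1: what 10% of values can mean.** Five scores on 60 patients make 300 values, and 10% is 30. If all losses fall at weeks 3 and 4 (120 values), that is 30/120 = 25% of those scores. A modest overall percentage can therefore be a large share of the late scores, on which the treatment comparison depends.

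**Step 2: the ANOVA.** Group-by-time test, no true effect, 1,500 simulated trials per setting. Monte Carlo error is 1.96 × √(0.05 × 0.95 / 1,500) = 0.011, or about 1.1 points. Each range covers both correlations. The single-imputation column also covers deterministic and noise-added versions.

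| Values missing | Patients complete | Single imputation, counted as observed | Mixed model, observed scores | Complete cases only |
|---|---|---|---|---|
| 3% | about 90% | 6.6-7.2% | 5.3% | 5.0-5.3% |
| 6% | about 81% | 8.7-9.6% | 4.7-4.8% | 4.7-5.3% |
| 11% | about 65% | 13.4-15.7% | 5.1-5.2% | 4.9-5.0% |

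A separate simulation gave about 6%, 9% and 13% at 3%, 6% and 10% missing. Together the ranges are 6-7%, 9-10% and 13-16%.

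**Step 3: the Hypothesis 3a t-test, 10% missing at week 4 (3 of 30 per arm).** Let m be the missing share. Under single deterministic imputation the variance estimate shrinks by roughly (1 − m), and n is counted instead of n(1 − m). The nominal standard error is then about (1 − m) = 0.9 of the true one. Approximate error: 2 × [1 − Φ(1.96 × 0.9)] = 2 × [1 − Φ(1.764)] = 7.8%. Simulations that impute from baseline agree: 7.1% to 7.4% for the change-score t-test and 8.2% for the baseline-adjusted comparison.

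**Step 4: does adjusting the degrees of freedom help?** Taking off one degree of freedom per imputed score gives 58 − 6 = 52. The critical value moves only from 2.002 to 2.007, whereas the standard error is about 10% too small. Simulated error after this change stayed at about 7.0-7.5%. If the observed counts are also carried into the variance and standard error, it falls to about 4-5%.

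**Step 5: power, true week-4 effect 0.5 SD (group-by-time test).** With 6% of values missing, complete-case ANOVA against mixed model is 30% against 33% (correlation 0.5) and 47% against 51% (0.7). With about 12% missing it is 22% against 25%, and 35% against 44%.

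**The case against.** **The target is exploratory.** This stands. The ANOVA decides no hypothesis, and the point has weight mainly because the Hypothesis 3a test shares the imputation rule.

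**Nothing in the plan says single imputation.** This also stands. A reader might infer that the ANOVA forces a choice between dropping incomplete patients and treating imputed scores as real. The documents do not support that: multiple imputation with pooled tests is a third route, and the wording leaves it open. The t-test adjustment could likewise be carried out in a way that works, as Step 4 shows, but the text names only degrees of freedom.

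**Patients would not be dropped.** Correct. The plan says it will impute, so losses calculated for a complete-case analysis describe a route it does not take. In the simulations that route cost some power but kept the error at 5%, with no material bias in the treatment difference.

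**Using only baseline and week 4 for Hypothesis 3a is not a mistake.** Agreed. A reader might infer that ignoring weeks 1 to 3 is an error. But section 1.2 defines the hypothesis as change from baseline to week 4, and the t-test addresses exactly that. The intermediate scores help mainly where week 4 is missing.

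**The simulation favours the mixed model.** Partly true: it was fitted with the correct covariance structure, and the correlation and dropout pattern are assumed. The inflation under single imputation does not depend on that advantage.

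**Conclusion.** The concern holds in limited form. The plan leaves open whether imputed scores will be treated as data. If they are, the trajectory ANOVA rejects a true null about 6-7% of the time with 3% of values missing, 9-10% with 6% and 13-16% with 10-11%. The Hypothesis 3a t-test rejects about 7-8% of the time with 10% of week-4 scores missing, and a degrees-of-freedom change alone does not cure it.

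These sizes rest on 30 per arm, correlation 0.5-0.7 and, for the ANOVA, dropout confined to weeks 3 and 4. The top of the ANOVA range lies at or just beyond the plan's 10% ceiling and implies about 35% of patients with an incomplete record. With very few missing values the effect is small.

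The mixed model held 4.7-5.3% in every setting, under the missing-at-random assumption the plan already makes. It is therefore a better method at low cost, not merely added detail. It does not bring back patients excluded by the 2-week rule for the modified intent-to-treat sample.

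**What to change.** Replace the repeated-measures ANOVA with a likelihood-based mixed model for repeated measures on all observed weekly scores, without imputation:

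- **Terms:** arm, week, arm-by-week, baseline score and baseline-by-week, with weeks 1 to 4 as outcomes.
- **Covariance:** unstructured, with a small-sample degrees-of-freedom method such as Kenward-Roger.
- **Scales:** a diagnosis term for SPS only. Model Y-BOCS and YGTSS separately and without it, because each scale is given to its own diagnostic group and the term would be constant or nearly so.
- **Hypothesis 3a:** take the week-4 arm contrast for SPS from this model. The question remains change from baseline to week 4.

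If imputation is kept here or for any other analysis, state that it is multiple, name the predictors and the number of imputations, and give the pooling rule for both t-tests and ANOVAs.

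The cost is a paragraph of analysis-plan text and a little more analysis work. SAS is already named for the behavioral data (section 5), and the weekly scores are already scheduled. The one technical price is estimating an unstructured covariance in about 60 patients, and in fewer for Y-BOCS and YGTSS.

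### Section 4.2 chooses covariates by observed imbalance, from an open list with no criterion, and never says whether the unadjusted or the adjusted result decides Hypotheses 2 and 3a

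*Combined protocol and SAP*

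**What the plan says.** All the relevant text is in section 4.2 of the combined protocol and SAP.

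- **Base tests.** For Hypothesis 2 (task fMRI), "Two-sample t-tests will compare ondansetron and placebo groups on change in activation over the 4-week trial". For Hypothesis 3a, "Two-sample t-tests will compare ondansetron and placebo groups on SPS change scores". Connectivity change is also compared by two-sample t-tests. On error rate, "Alpha level will be set at 0.05 for all analyses".
- **Baseline values of the outcome.** Each outcome type has its own trigger for a follow-up adjusted ANOVA. For task activation it is "if there are significant baseline differences between the groups within the insula and somatosensory ROI". For symptoms the wording is "If there are baseline differences between the groups in any of the symptom scales (SPS, Y-BOCS, or YGTSS), follow-up one-way ANOVAs", with no threshold. For connectivity, "baseline differences will be probed using t-tests and included as covariates in follow-up ANOVAs if necessary".
- **Everything else.** Under Additional post-hoc analyses there is a separate and wider rule: "Any clinical or demographic differences remaining between the groups after randomization including age, gender, illness duration, and medication dosage" "will be statistically controlled for in all analyses".

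The plan contains no fixed covariate set. It does not say whether the t-test or the adjusted model decides a hypothesis when both have been run.

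**The concern.** Under correct randomisation, differences between arms in age or illness duration are chance. Adjustment earns its place when a variable predicts the outcome, whether or not it happens to be imbalanced. A rule that adjusts only on observed imbalance leaves out prognostic variables in most trials, and so gives up precision that a trial of about 60 patients could use.

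The wording is also loose in three ways. The four variables are examples, so the list has no end. No test, threshold or standardised difference defines a difference. And the stated reach is every analysis, although the tests named for Hypotheses 2 and 3a are unadjusted. Two analysts following this plan could report different primary results, and both could say they had kept to it.

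**Working it through.** **Inputs from the documents.** 30 patients from each of two sites, so 60 (section 2.1.1); two randomised groups (section 4.1); alpha 0.05 and missing data of 10% or less (section 4.2). The plan gives no effect size, SD or power, so there is no figure of its own to reproduce.

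**Assumptions.** 1:1 allocation, two-sided tests, normal covariates, and a standardised difference of 0.7. The share of outcome variance that the covariates explain (R²) is unknown and is varied.

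**Step 1: how often the rule is triggered.** For k independent comparisons at p<0.05 the chance of at least one difference is 1 − 0.95^k.
- Four named variables: 1 − 0.95^4 = 18.5%. Simulation with correlation 0.3 gives 16.7%. Hence 17-19%.
- Adding SPS, Y-BOCS and YGTSS: 1 − 0.95^7 = 30.2%.
- With p<0.10 as the criterion: 1 − 0.90^4 = 34.4% and 1 − 0.90^7 = 52.2%.

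**Step 2: type I error if the rule is applied mechanically.** Null trials were simulated with four independent covariates, R² from 0 to 0.6, and 60 or 54 patients (54 being 10% fewer). Adjusting for whatever differs at p<0.05 rejects in 3.1-5.3% of trials. It is conservative when the covariates are prognostic. Pre-specified ANCOVA gives 4.2-5.4%, which is nominal within simulation error.

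**Step 3: power.** The noncentrality of the t-test is 0.7 × √(30/2) = 2.711. With the critical value 2.002 (58 df), power is about Φ(2.711 − 2.002) = 76%; the normal approximation gives 77.4%. Simulation of the imbalance-triggered rule gives 76.7% at R² = 0.2 and 76.8% at R² = 0.4, about the same as never adjusting.

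For ANCOVA with k fixed covariates the variance is multiplied by (1 − R²)(N − 3)/(N − 3 − k). With k = 5 (baseline outcome plus four) the last factor is 57/52 = 1.096, and the critical value on 53 df is 2.006:

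| R² | Variance factor | Noncentrality | Power |
|---|---|---|---|
| 0 | 1.096 | 2.589 | 72% |
| 0.1 | 0.987 | 2.730 | 77% |
| 0.2 | 0.877 | 2.895 | 81% |
| 0.4 | 0.658 | 3.343 | 91% |

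Simulation with four covariates gives 82.9% at R² = 0.2 and 90.7% at R² = 0.4. The variance breaks even at R² = 1 − 52/57 = 9%.

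**Step 4: what the discretion could do.** Suppose both results are computed and the better is reported, with ten covariates and joint R² 0.2. As the imbalance threshold runs from 0.05 to 0.20, simulated type I error is about 5-7% with independent covariates and about 6-8% with correlation 0.3. With four independent covariates at p<0.05 it is 4.7-5.9%.

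**The case against.** The sentence is mandatory, not permissive: differences are to be controlled for. It works on patient characteristics, not outcomes, and the base tests are named. As written, then, it keeps the error rate. That stands.

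Three stronger readings are tempting, and the documents do not support them.

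- *The primary model is chosen from the outcome data.* Nothing says so. What is missing is a criterion and a time for the choice. The analysis set is patients who complete at least two weeks of treatment, so the final groups are known only after follow-up has begun, and nothing places the check before outcomes are seen. That is a gap, not evidence of outcome-driven selection.
- *The model will more likely than not change.* That needs about 20 independent or mildly correlated measures (1 − 0.95^20 = 64%; 55% at correlation 0.3). The plan gives no such count and does not say that every questionnaire is a candidate. For the four variables it names, the figure is 17-19%.
- *The error rate is seriously inflated.* Free choice among all 2^4 = 16 subsets of the named variables would give 7-18% in simulation, but the plan describes no such search. Even reporting the better of two results is not planned; it is only not ruled out.

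It can also be said that the sentence sits under a post-hoc heading. The placing does leave its scope unclear, but the words cover every analysis, and nothing exempts Hypotheses 2 and 3a.

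**Conclusion.** The point holds as a weakness in the analysis rule, worth correcting before unblinding. It is not a threat to validity. The definite defects are the open list, the absent criterion and the unnamed deciding analysis.

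The main cost is forgone power: about 4-6 percentage points if covariates explain 20% of variance and about 14 if they explain 40%, with no real gain at 10% or less. This rests on a standardised difference of 0.7 and 30 per arm. Type I error stays at about 3-5% under mechanical use at p<0.05. The 5-8% figure requires selective reporting, and its upper end also requires a lenient threshold and correlated covariates. None of those inputs comes from the documents.

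**What to change.** Amend the four analysis paragraphs of section 4.2 together (group-level fMRI, clinical symptoms, resting-state connectivity, additional post-hoc). Editing only the last would leave the t-tests in conflict with it.

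1. Name one ANCOVA as the deciding analysis for each Hypothesis 2 and 3a comparison.
2. Include the baseline value of that outcome and a short closed list of baseline covariates, fixed before unblinding and used whatever the observed balance. The four variables the plan already names (age, gender, illness duration, medication dosage) would serve as the list.
3. Drop imbalance, tested or inspected, as the way of choosing covariates.
4. Label the unadjusted t-test and any further adjustment as sensitivity analyses.

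**Cost.** A few sentences in four paragraphs, and four to five degrees of freedom out of 58. If the covariates prove unrelated to the outcome the price is small but not zero: about 4 points of power in the table above (76% to 72%). A chance imbalance in an unlisted variable would be handled only in a sensitivity analysis.
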